This device is for single-use only and should not be re-used. Re-use may lead to increased risk of infection or cross contamination. Physical properties of the device may no longer be opti mal for intended use.

Appropriate supportive measures should be taken where indi-cated (e.g. use of graduated compression bandaging in the management of venous leg ulcers or pressure relief measures in the management of pressure ploers/spres).
The control of blood glucose, as well as appropriate supportive

me control of pricose, as well as appropriate supportive measures, should be provided with diabetic foot ulcers. Infection is not a contraindication to the use of AQUACEL EXTRA Hydrofiber Dressing with Strengthening Fibre. Should infection develop during the use of the dressing, antibiotic therapy should be intilated, as clinically indicated, by a health care professional, AQUACEL EXTRA Hydrofiber Diessing with Strengthening Fibre

can facilitate the control of minor bleeding.

If removing the drawing is difficult, the dressing should be fully saturated with sterile saline or water and removed slowly. Secure ACQUACEL EXTRA Hydrofiber Dressing with Strengthening Fibre provides a most environment that sup-ports the growth of new blood vessels, occasionally the delicate newly formed blood vessels may produce a blood stalined bluft brum

AQUACEL EXTRA Hydrofiber Dressing with Strengthening Fibre

is not intended for use as a surgical sponge. AQUACEL EXTRA Hydrofiber Dressing with Strengthening Fibre is not intended for use within internal body cavities or within dased wounds

DIRECTIONS FOR USE

1. Exuding Wounds (Excluding Partial Thickness Burns)

- Before applying the dressing, Cleanse the wound area with an appropriate wound cleanser. AQUACEL EXTRA Hydrofiber Dressing with Strengthening Fibre

- AQUACEL EXTRA Hydrofiber Dressing with Strengthening Fibre should overlap 1 cm onto the skin surrounding the wound. Apply the dressing to the wound and over with a moisture retentive dressing (e.g., DuoDERM* Extra Thin or Versiva* XC), or other appropriate secondary dressing. See relevant individual package inserts for complete instructions for use. All wounds should be inspected frequently. Remove the AQUACEL EXTRA Hydrofiber Dressing with Strengthening Fibre when clinically indicated (i.e., leakage, excessive bleeding, or suspicion of infection).

 AQUACEL EXTRA Hydrofiber Dressing with Strengthening Fibre
- AQUACEL EXTRA Hydrofiber Dressing with Strengthening Fibre can be left in place for up to 7 days, where clinically indicated, lexcept in burns and donor sites where it can be left in place for

2. Dry Wounds

- 2. Dry Wounds
 In addition to the directions for use set forth above:

 Place the AQUACEL EXTRA Hydrofiber Dressing with

 Strengthening Fibre on the wound and wet with sterile water
 or saline over the wound area only.

 Cover the dressing with a moisture retentive dressing such as

 DuoDERAM Extra Thin to avoid drying out of the dressing and
 subsequent dressing adherence to the wound.

3. Partial thickness burns

- Before applying the dressing, cleante the wound area with an appropriate wound cleanser.
- appropriate wound cleanser.

 The AQUACEL EXTRA Hydrofiber Dressing with Strengthening Fibre should overlap at least 5cm onto the skin surrounding the burn or other adjacent AQUACEL EXTRA Hydrofiber Dressing with Strengthening Fibre, as the dressing will shrink as it. absorbs the exudate
- absorbs the exudate. The AQUACEL EXTRA Hydrofiber Dressing with Strengthening Fibre should be covered with a stenie loosely woven gause pad and appropriately secured. In the immediate post burn period (up to 4 days) large volumes of wound coudate may require that the saturated dressing be removed and replaced with new
- AQUACEL EXTRA Hydrofiber Dressing with Strengthening Fibre.

 Remove the cover periodically and inspect the AQUACEL EXTRA
 Hydrofiber Dressing with Strengthening Fibre while it remains
 in place on the burn.
- in this indication adherence to the wound bed of the ACMACEL EXTRA Hydrofiber Dressing with Strengthening Fibro is a desired characteristic. Non adherence of areas of the dressis a destried characteristic, fron adherence or areas or the dressing may indicate deopening of the wound or infection. Areas of the dressing may be cut away to facilitate assessment. The exposed areas should then be treated appropriately. As the burn wound re-epithelialises, the AQUACEL EXTRA Hydrofiber Dressing with Strengthening Fibre will detach or be easily removed.
- regarding the state of the stat

Discard any unused portion of the dressing

Store in cool dry glace. (10°C - 25°C/50°F ~ 77°F).

If further information or guidance is needed, please contact Convalled Professional Services

© 2016 ConvaTed Inc.
*/**indicates a tracemark of ConvaTed Inc.

DEUTSCH

PRODUKTBESCHREIBUNG:

PRODUKTBESCHREIBUNG:
Der AQUACEL "EXTRA" Hydrofiber" Verband mit
Verstarkungsfasern ist eine welche, sterke, nicht gewebte
Wundauflage aus Natriumcarboxymethylzeilulose und chemisch
veränderten Cellulosefasern zur Verstärkung. Dieser stark
absorbiarnade Verband nimmt Wundexstedat auf und bildet ein
veränderten Gel. Durch das Gel wird die Wonde feucht gehalten und
ein optimales Wundheilungstmillen geschaffen. AQUACEL
unterstützt den Helungsprozell und erleichtet den Arcansport von
abgestorbenem Gewebe aus der Wunde (autolytisches
Debridement) ohno Beschädigung des neugebildeten Gewebes.

INDICATIONEN:

Unter Aufsicht von medizinischem Fachpersonal kann der AQUACEL EXTRA Hydrofiber Verband mit Verstärkenden Fasarn ingesetzt werden zur Behandlung von: Geinoeschwüren, Druckaeschwüren (Grad (HV) und

Appendix 4: CEAP Classification

(1)

C class	Description
Co	No visible or palpable signs of venous disease
Ci	Telanglectasias or reticular veins
C2	Varicose veins
C ₂ ,	Recurrent varicose veins
C ₃	Edema
C4 Mind Market Company Street Company	Changes in skin and subcutaneous tissue secondary to CVD
C48 Y 35 / 1 1 1 1 1 1 1 1 1 1 1 1 1 1 1 1 1 1	Pigmentation or eczema
C _{4b}	Lipodermatosclerosis or atrophie blanche
C4c	Corona phlebectatica
C _s	Healed
Co the said the said the	Active venous ulcer
C _{6r}	Recurrent active venous uicer

Appendix 5: IWGDF/IDCA Guideline

(15, 16)

Clinical manifestations	Infection severity	PEDIS grade
Wound lacking purulence or any manifestations of inflammation	Uninfected	
Presence of ≥2 manifestations of inflammation (purulence, or erythema,	Mild	2
tenderness, warmth, or induration), but any cellulitis/erythema extends <2cm		
around the ulcer, and infection is limited to the skin or superficial		
subcutaneous tissues; no other local complications or systemic illness		
Infection (as above) in a patient who is systemically well and metabolically	Moderate	3
stable but which has ≥1 of the following characteristics: cellulitis extending		
>2cm, lymphangitic streaking, spread beneath the superficial fascia, deep-		
tissue abscess, gangrene, and involvement of muscle, tendon, joint or bone		
Infection in a patient with systemic toxicity or metabolic instability (e.g. fever,	Severe	4
chills, tachycardia, hypotension, confusion, vomiting, leukocytosis, acidosis,		
severe hyperglycemia, or azotemia)		

[figure not shown]
Appendix 6: Venous Leg Ulcers – signs of infection

[figure not shown]
(15)

[figure not shown]
2 or more of the following criteria:

Signs of infection	Yes	No
New pain, increasing pain, or altered pain in the ulcer area;		
Malodor		
Increase in ulcer area		
Wound breakdown		
Delayed or non-healing	 	
Erythema		
Increase in local temperature		

Appendix 7: Coloplast Wound assessment Form

Appendix 8: Quality of Life (EQ-5D-5L)

Health Questionnaire (EQ-5D-5L)

Under each heading, please tick the ONE box that best describes your health TODAY.

[figure not shown]
MO	BILITY
$[]_1$	I have no problems in walking about
	I have slight problems in walking about
\square_3	have moderate problems in walking about
4	I have severe problems in walking about
5	I am unable to walk about
SEL	F-CARE
\square_1	I have no problems washing or dressing myself
2	I have slight problems washing or dressing myself
3	I have moderate problems washing or dressing myself
\square_4	I have severe problems washing or dressing myself
5	am unable to wash or dress myself
USL	JAL ACTIVITIES (e.g. work, study, housework, family or leisure activities)
-9	I have no problems doing my usual activities
2	I have slight problems doing my usual activities
3	I have moderate problems doing my usual activities
4	I have severe problems doing my usual activities
5	I am unable to do my usual activities
PAI	N / DISCOMFORT
	I have no pain or discomfort
2	I have slight pain or discomfort
	I have moderate pain or discomfort
	I have severe pain or discomfort
_ s	I have extreme pain or discomfort
KNA	(IETY / DEPRESSION
1	am not anxious or depressed
2	I am slightly anxious or depressed
\Box_3	I am moderately anxious or depressed
4	l am severely anxious or depressed
5	I am extremely anxious or depressed

UK (English) © 2009 EuroQol Group EQ-5D™ is a trade mark of the EuroQol Group

Health Questionnaire (EQ-5D-5L)

- We would like to know how good or bad your health is TODAY.
- This scale is numbered from 0 to 100.
- 100 means the best health you can imagine.
 0 means the worst health you can imagine.
- . Mark an X on the scale to indicate how your health is TODAY
- Now, please write the number you marked on the scale in the below.

YOUR HEALTH TODAY =

UK (English) © 2009 EuroQol Group EQ-5D™ is a trade mark of the EuroQol Group

Appendix 9: Endpoints and assessments

	Endpoints and assess- ments	Assessed by	V1 (Base- line)	V2	V3	V4	V5 (Termina- tion)
Primary end- point	Percentage wound area reduction during the investigational test period of four weeks	Investiga- tor/ delegate		x	X	x	X
Secondary endpoint	Total treatment costs during the investigational test period based on the number of dressing used during the investigation and the unit price of the products	Investiga- tor/ delegate	x	x	x	x	x
Exploratory endpoints	Percentage wound depth reduction during the investigational test period	Investiga- tor/ delegate	x	х	x	x	x
	Wound bed, wound edge and peri wound skin condition based on visual assessment based on the Coloplast Wound Assessment Form	Investiga- tor/ delegate	x	x	x	x	х
	Conformability of the dressing based on PI or delegates evaluation according to a 5-point Liker scale	Investiga- tor/ delegate			x		x
	Responder defined as a subject reaching ≥ 30% wound area reduction within the 4-week investigational test period (yes/no)	Data Manage- ment					x
	Wound healed during the investigation pe- riod (yes/no)	Investiga- tor/ delegate		x	x	x	x
	Quality of Life evalu- ated by EQ-5D-5L	Subject	х				x
Safety Assessments	Averse events Device Deficiencies	Investiga- tor/ delegate	x	x	х	x	х

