5.1. General

The clinical investigation is a two-arms, open-labelled, stratified, randomized, controlled, multicentre investigation comparing the clinical performance of Biatain® Silicone with standard of care in chronic wounds with wound depth down to 20 mm.

In total 100 eligible subjects will be randomised to one of two groups receiving either Biatain® Silicone or Mepilex® Border and AQUACEL® EXTRA™ Hydrofiber® Dressing.

Subjects will be stratified according to one of the two chronic wound types: venous leg ulcers or diabetic foot ulcers to account for differences in healing patterns. The subjects will be enrolled at >12 sites in the UK.

The subjects will have a weekly scheduled visit, V1-V5 (- 2 days) during a four-week investigational test period where the wound will be assessed, and the investigational test product or comparator products will be applied. Furthermore, the subject will respond to a questionnaire and discuss any adverse events. (Figure 4 shows the design of the clinical investigation). If needed, unscheduled visits can be performed between the weekly scheduled visits. The weekly scheduled site visits can be performed at the subject's home if the site provides this service. Sites conducting visits at patients' homes, should follow the NHS Lone Working Policy and any applicable local Trust procedures. Many wound care patients have reduced mobility and some tissue viability services conduct home visits as part of usual care. Home visits for this study should only be conducted at sites where such visits are part of routine care and usual service.

[figure not shown]

Figure 4: Design of the clinical investigation

Eligible subjects are invited to a Screening Visit (V0). The subjects will be consented prior to any study related procedures. The subjects must be given at least 24 hours to consider their participation, but if the subjects wish to, the Screening visit (V0) and Baseline (V1) visit can be combined and performed on the same day. V0 can be done remotely.

Informed Consent will be signed at the Baseline Visit (V1). After the 4-week investigational test period, a termination visit (V5) will be conducted to complete all 4 test weeks.

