5.6. Demography and potential compromising factors

The following baseline data will be collected and reported at the Baseline Visit (V1) by the Principal Investigator or delegate:

- Age (years) at time of inclusion
- Height (cm)
- Weight (kg)
- Gender (male/female)
- Smoking (yes/no)
- Alcohol (units per week)
- Comorbidities affecting wound healing (diabetes, venous insufficiency, peripheral arterial disease, cardiopulmonary conditions, immune deficiencies, dementia or other as assessed relevant by investigator)
- Concomitant medication
- Wound type (VLU or DFU)
- Duration of wound (date of onset)
- Wound dressing at time of inclusion
- Wound size (measured by photo uploaded in a digital photo-planimetry software system)

Wound depth (mm)

To ensure optimal conditions for wound healing for VLUs, compression therapy must be performed, according to standard of care, such as compression therapy-bandage, compression sock, or other.

To ensure optimal conditions for wound healing for DFUs, off-loading must be performed according to standard of care based on subject need (wound location), preference and resources available. Methods of off-loading must be documented. Common methods to off-load the foot include bed rest, wheelchair, crutch-assisted gait, total contact casts, felted foam, half shoes, therapeutic shoes, and removable cast walkers.

Subjects who may require another dressing than the investigational test product(s) (e.g., an antimicrobial dressing superabsorbent dressing or other) will be followed during the four weeks follow-period. If other relevant wound care products are required to be used in addition to the test products, as part of standard of care (e.g., barrier cream), this must be recorded.

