5.8. Randomization Procedure

All included subjects that meet the inclusion and exclusion criteria will be randomized to one of two treatment groups. Randomization will be centralized using Medidata RAVE and stratified based on wound type (VLU or DFU).

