Analysis of the primary endpoint:

The percent wound area reduction (WAR) will be analyzed by an analysis of variance with treatment and wound type (VLU and DFU) as fixed effects and wound area at baseline as covariate.

The mean WAR for each treatment group will be estimated together with the 95% confidence interval. Further, the difference in mean including a 95% confidence interval between the 2 treatments will be estimated.

Analysis of the secondary endpoint:

The secondary endpoint, total cost, will be calculated as the number of products used during the investigational period multiplied by the unit price of the product. Unit price will be extracted from Drug Tarif on the date of Last Patient Out.

This secondary endpoint will be analyzed by comparing the mean cost in the two groups assuming the cost data to be normally distributed. It will be tested on a 2-sided 5% test level if the difference in mean between the two treatments is zero. Further, the mean cost for each treatment will be estimated together with a 95% confidence interval.

Analysis of exploratory endpoints:

Percentage wound depth reduction will be analyzed by the same model as described for the primary endpoint but with wound depth at baseline as covariate.

Similarly, the two endpoints related to EQ-5D-5L (the index score and the VAS score) will be analyzed by an analysis of variance with treatment as a fixed effect and the baseline measure as covariate.

The two endpoints; responder defined as a subject reaching ≥ 30% wound area reduction within the 4-week investigation period (Yes/No) and wound healed during the investigation period (Yes/No) will be analyzed by a logistic regression model with treatment and wound type (VLU or DFU) as fixed effects and wound area at baseline as covariate.

Analysis of safety endpoints:

Adverse events will be listed and summarized, if relevant. Device deficiencies and concomitant medication will be listed.

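### The EQ-5D-5L models in section 10.1 omit wound type, the only randomisation stratum; adding it is a small, free gain in precision

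*Combined protocol and SAP*

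**What the plan says.** Section 5.8 describes central randomisation that is "stratified based on wound type (VLU or DFU" and names no other factor. Section 5.1 gives the reason for stratifying: "to account for differences in healing patterns".

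Section 10.1 gives the analysis models:

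- **Area reduction (primary):** treatment, wound type and baseline area.
- **Depth reduction:** the primary model, with baseline depth in place of baseline area.
- **Responder and healed:** logistic regression with treatment, wound type and baseline area.
- **EQ-5D-5L index and VAS:** "analysis of variance with treatment as a fixed effect and the baseline measure as covariate".

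The EQ-5D-5L sentence is introduced as parallel to the depth model before it, yet wound type is missing and no reason is given. Appendix 9 lists "Quality of Life evalu- ated by EQ-5D-5L" as an exploratory endpoint, and both it and Table 4 place the questionnaire at V1 and V5. Section 10.1 specifies 95% confidence intervals for area reduction and cost, but names none for EQ-5D-5L.

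**The concern.** When randomisation is stratified by a factor, the analysis normally includes that factor. If the arms are balanced within wound type, differences between the two types contribute nothing to the true error of the treatment difference. A model without wound type still leaves those differences in the residual variance and so overstates the standard error.

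The documents make some effect on quality of life plausible. The EQ-5D-5L asks about mobility, self-care, usual activities and pain (Appendix 8, for example "I have severe problems in walking about"). Subjects with DFUs are off-loaded (5.6: "Common methods to off-load the foot include bed rest, wheelchair, crutch-assisted gait, total contact casts"), while subjects with VLUs receive compression. If the two types heal differently over four weeks, their scores could also change differently.

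What is at stake is precision on the only patient-reported endpoints, which 10.1 uses to explore the primary objective further.

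**Working it through.** **Inputs.** From the documents: 40 completers per arm, so 80 in all (10.2; enrolment 80/(1 − 0.20) = 100 reproduces); wound type as the only stratum (5.8); two-sided 5% level (10.3); VLU/DFU split left open (6.2.1). The plan gives no EQ-5D-5L standard deviation, no precision target and no wound-type effect, so there is no stated figure to reproduce. The following are assumptions, shown as ranges: the wound-type effect, the V1–V5 correlation, the split (50:50 or 70:30) and permuted blocks of 4 within wound type.

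10.1 does not say whether the outcome is the V5 score or the change from V1. With the V1 score as covariate the treatment difference is the same either way.

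**Step 1, approximate formula.** Let r be the partial correlation of wound type with the V5 score given the V1 score. With arms balanced within wound type:

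- width without wound type / width with it ≈ 1/√(1 − r²)
- coverage of the nominal 95% interval ≈ 2Φ(1.96/√(1 − r²)) − 1

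For a 50:50 split, the gap d between wound types in residual SDs solves r² = 0.25d²/(1 + 0.25d²), so d = 2r/√(1 − r²).

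| r | d (50:50) | width ratio | excess width | coverage |
|---|---|---|---|---|
| 0.2 | 0.41 | 1/√0.96 = 1.021 | 2% | 95.5% |
| 0.3 | 0.63 | 1/√0.91 = 1.048 | 5% | 96.0% |
| 0.4 | 0.87 | 1/√0.84 = 1.091 | 9% | 96.8% |

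**Step 2, simulation of an effect independent of baseline.** 80 completers, V1–V5 correlation parameter 0.6, 6,000 trials per setting. The Monte Carlo error of a coverage figure is about √(0.95 × 0.05/6000) = 0.28 percentage points.

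| gap d (residual SD) | excess width, 50:50 | excess width, 70:30 | coverage without wound type, 50:50 | coverage with wound type, 50:50 |
|---|---|---|---|---|
| 0 | −0.04% | −0.03% | 95.3% | 95.3% |
| 0.2 | 0.4% | 0.4% | 95.5% | 95.3% |
| 0.5 | 3.1% | 2.6% | 95.7% | 95.0% |
| 0.8 | 7.8% | 6.5% | 96.4% | 95.0% |
| 1.0 | 12.0% | 10.1% | 97.0% | 94.8% |

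**Step 3, simulation where the gap already exists at V1.** 50:50 split, correlation 0.5 or 0.7, baseline gap 0.3 to 0.8 SD, 5,000 trials per setting.

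- Same gap at V1 and V5: excess width 0.15% to 2.2%.
- Wound type acts only through the V1 score: excess width −0.05% to −0.15%, that is, none.

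**Step 4, cost of the extra term.** Residual degrees of freedom fall from 80 − 3 = 77 to 80 − 4 = 76. Where wound type adds nothing, the simulated interval widens by about 0.15% at most.

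**The case against.** The strongest objection is that the V1 score already carries most of what wound type would explain. Subjects must accept compression or off-loading to enter, and the wound must have lasted more than 8 weeks (6.1.1, criteria 7 and 3). Compression and off-loading are recorded at the same V1 visit as the first EQ-5D-5L (7.2, Table 4). Differences in mobility and pain are therefore largely in the covariate, which is the situation in Step 3. The reason for stratifying in 5.1 concerns healing, not quality of life. This stands, and it puts the likely loss nearer 0–3% than 9%. It does not remove the point: differential healing between V1 and V5 could still move the scores, and the term costs almost nothing if it does not.

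Three stronger readings are tempting, and the documents do not support them.

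- *The EQ-5D-5L intervals will over-cover.* This needs balance within wound type. Section 5.8 states no blocking method; without blocking, coverage would be nearer nominal, although adjustment would still narrow the interval when wound type is prognostic. Nor does 10.1 promise an EQ-5D-5L interval; the argument applies to the standard error and test in any case.
- *The omission tilts the trial towards finding the dressings comparable.* The rule in 10.4 uses wound area and total cost only, and there is no quality-of-life comparability rule. A wider interval makes a difference harder to detect, but equally harder to exclude.
- *About 16% of the sample is wasted.* That is r² at r = 0.4 (0.4² = 0.16), which needs a gap of about 0.87 residual SD after baseline adjustment. No figure in the documents supports an effect that large.

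**Conclusion.** The inconsistency is real: among the endpoints with a stated regression model, only the EQ-5D-5L pair leaves out the stratification factor. The consequence is a possible loss of precision, with no bias and no inflation of type I error. The loss arises only if wound type predicts the V5 score beyond the V1 score. The excess width is about 0–3% in moderate scenarios, about 9% at an assumed partial correlation of 0.4, and nil if wound type acts only through baseline. These figures assume 80 completers and arms balanced within wound type; the effect sizes are assumed, not taken from the plan. Because the endpoints are exploratory and outside the pass/fail rule, this is a minor improvement worth making because it is free.

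**What to change.** In section 10.1, replace the EQ-5D-5L sentence with wording such as: *The V5 index score and the V5 VAS score will each be analysed in a linear model containing treatment, wound type (VLU or DFU) and the corresponding V1 score; the adjusted treatment difference will be reported with its 95% confidence interval.* This gives the pair the same structure as the area and depth models, names the outcome visit and makes the interval explicit.

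The cost is one sentence and one of 77 residual degrees of freedom. Wound type is already recorded at V1 and used for randomisation, so no new data, visits or subjects are needed. The change should be made before database lock, while the trial statistician is still blinded (5.9).

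In the same edit, the sponsor could consider the cost comparison in 10.1. It is also described without wound type and, unlike EQ-5D-5L, it feeds the rule in 10.4.
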